TRANEXAMIC ACID FOR cSDH-

A PILOT STUDY ON THE SAFETY OF TRANEXAMIC ACID FOR THE CHRONIC SUDURAL HEMATOMA POPULATION

NCT02618382

Tranexamic acid for cSDH – A Pilot Study on the Safety of Tranexamic Acid for the Chronic Subdural Hematoma Population

Study Objectives

1. Establish the safety of using tranexamic acid in the treatment of chronic subdural hematomas
2. Determine if the use of oral tranexamic acid reduces the rate of ipsilateral recurrence following drainage of chronic subdural hematomas

Background

Chronic subdural hematomas are a common problem faced by neurosurgery with an annual incidence of 13.5/100,000 persons per year and up to 58/100,000 in the over 65 years old population (Kudo). Their treatment is often complicated by recurrence with rates reported as high as 33% (Muzii). Currently there is no good strategy to help avoid this problem, which adds significantly to patient morbidity. The pathogenesis of this problem is believed to be related to the propensity of the associated neo-membranes to bleed (Ito, Weir, Lim, Labadie). Ito et.al. showed with labeled red blood cells that bleeding continues to occur into the hematoma cavity (1976). It has also been shown that there are high levels of tissue plasminogen activator in the outer membrane of chronic subdural hematomas (Ito 78 and Labadie 74). Lim et.al. found that ratio of tissue plasminogen activator to plasminogen activator inhibitor contributed to the pathogenesis (Lim 95). It has also been shown that chronic subdural hematomas have high levels of fibrin degradation products which in addition to marking the breakdown of fibrin are themselves anti-hemostatic by enhancing tissue plasminogen activator activity (Nieuwenhuizen 83), having an anti-thrombin affect (fletcher 62) and inhibiting platelet aggregation (kowalski 64) and fibrin polymerization (Alkjaersig 62). Essentially, a scenario of ongoing hemorrhage and repeated clot formation and hyperfibrinolysis leads to the expansion and recurrence of chronic subdural hematomas.

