Exclusion Criteria

- cSDH not requiring surgical drainage
- patients undergoing bedside twist drill craniostomy
- medically unstable for surgery
- patients requiring long-term anticoagulation- unable to stay off for less than 30 days
- patients not expected to survive to the completion of follow-up
- patients comatose prior to the initiation of treatment
- history of thromboembolic problem including stroke, MI, DVT, PE
- pregnant
- minor
- allergy/sensitivity to tranexamic acid
- irreversible coagulopathy
- known clotting disorder
- bilateral hematomas with both requiring drainage
- incarcerated
- any patient not judged suitable for the study by the investigators
- women who are taking combination oral contraceptive

Study Enrollment

Patients meeting all of the inclusion and exclusion criteria will undergo standard treatment of their chronic subdural hematoma including operative treatment with the addition of preoperative and postoperative oral tranexamic acid treatment. Patients will receive a dose of 1300mg orally three to four hours prior to surgery. They will then take 1300mg orally three times daily for three days or until discharge, whichever occurs first. Tracking and follow-up will be explained to the patients and arranged by the study coordinator.

Tranexamic acid for cSDH – A Pilot Study on the Safety of Tranexamic Acid for the Chronic Subdural Hematoma Population

Study Interventions

All patients will undergo an intervention for the drainage of their subdural hematoma. The type of procedure i.e. burr-hole drainage or craniotomy excluding twist drill craniostomy will be at the discretion of the treating physician

All patients will be followed daily during their hospitalization

All patients will have follow-up CTs on postop days 1, 3, 7 and 30 +/- 7 days

All patients will have clinical follow-up on Day 30 +/- 7 days

All patients will be treated using standard ICU protocols

- neurologic status will be assessed at least every four hours for the first 48 hours
- care will be directed toward the goal of normotension and adequate oxygenation

All patients will have DVT prophylaxis with spontaneous compression devices. Pharmacologic prophylaxis will be at the discretion of the treating physician.

Experimental Interventions

Patients will receive tranexamic acid in the following dosing regimen:

1. 1300 mg times one immediately prior to surgery
2. 1300 mg orally three times daily for three days or until discharge- whichever comes first.

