-First postop dosing will start 8 hours after preop dose is given.

All patients will have creatinine monitored daily while on study drug. Patients with creatinine > 1.4 will have dosage adjustments as follows:

Table 1. Dosage of LYSTEADA in Patients with Renal Impairment

LYSTEADA		
Serum Creatinine (mg/dL)	Adjusted Dose	Total Daily Dose
Cr above 1.4 and \leq 2.8	1300 mg (two 650 mg tablets) two times a day for a maximum of 5 days during menstruation	2600 mg
Cr above 2.8 and \leq 5.7	1300 mg (two 650 mg tablets) once a day for a maximum of 5 days during menstruation	1300 mg
Cr above 5.7	650 mg (one 650 mg tablet) once a day for a maximum of 5 days during menstruation	650 mg

Prohibited Interventions

Therapeutic anticoagulation

Tranexamic acid for cSDH – A Pilot Study on the Safety of Tranexamic Acid for the Chronic Subdural Hematoma Population

Clinical and Laboratory Evaluations

Presentation Day 0- CT scan, NIH stroke scale, pregnancy test, informed consent, modified Rankin Score (mRS)

Postop-
Day 1 CT Scan

Day 14 clinical follow-up, CT scan

Follow-up Day 30- CT scan, NIH stroke scale, mRS

Timing of Evaluations

Registration- the start of the screening process when the study team is notified of a potentially eligible subject

Pre-Enrollment- all screening evaluations will be performed prior to enrollment

Enrollment- will occur prior to surgical intervention or receiving experimental medication

Medication period- Patients will continue on medication from immediately preoperatively to three days postoperatively or until discharge

Post Medication period- follow-up will continue until the patient is discharged from the neurosurgeon's care

Management of Adverse Events

All adverse events will be closely monitored and evaluated

Management of recurrent bleeding: recurrent SDHs will be managed according to best practices as determined by the treating physician

Criteria for Intervention Discontinuation

1. patient unable to tolerate side effects
2. thromboembolic complication including stroke, MI, DVT or PE
3. if in the investigator's judgment, withdrawal from the trial will be in the patients best interest
4. consent is withdrawn by the patient or their legal representative

End Points

1* Incidence of medication related complications including stroke, MI, DVT, or PE and other drug related adverse events

2- Return to OR for same sided surgery

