2* Postop hematoma expansion, functional outcome (mRS, NIHSS) discharge location, LOS, volume of hematoma at 30 days

Tranexamic acid for cSDH – A Pilot Study on the Safety of Tranexamic Acid for the Chronic Subdural Hematoma Population

Data Points

Age, presenting symptom, admission GCS, language and motor function, preoperative living situation, width of hematoma, visible septations present, extent of MLS, operative approach, drain used, new preoperative deficit, immediate postop hematoma width, LOS, discharge GCS, language and motor function, discharge location, width of hematoma on follow up imaging, medication not tolerated, medication side effects, thromboembolic complications, other complications, blood loss, NIH stroke scale Day 0 and 30, mRS day 0 and 30

Statistical Data Analysis

Frequencies will be reported for ordinal and categorical variables. Descriptive analyses of central tendency (mean) will be used for continuous variables. Nonparametric tests will be used for statistical comparison, including the Kruskal-Wallis rank-sum test for multiple groups and the Mann-Whitney U test for 2 groups. Data tabulation and analysis will be analyzed using R statistical software version 3.4.2 (R Foundation for Statistical Computing, Vienna, Austria). Chi-square test, analysis of variance (ANOVA), and multivariate linear and log-linear regression models where appropriate. A P value < 0.05 will be considered statistically significant. P values for difference among time point means (preoperative, postoperative days 3, 7 and 30) to be determined by ANOVA.

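### The postoperative CT schedule is stated in two ways that are not reconciled, and only one of them supplies the Day 3 and Day 7 scans that the planned ANOVA appears to need

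*Combined protocol and SAP*

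**What the plan says.** Study Interventions gives the imaging rule for every patient: "All patients will have follow-up CTs on postop days 1, 3, 7 and 30 +/- 7 days". It adds one clinical visit: "All patients will have clinical follow-up on Day 30 +/- 7 days".

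Clinical and Laboratory Evaluations gives a different list. After a Day 1 CT it has "Day 14 clinical follow-up, CT scan" and then "Follow-up Day 30- CT scan, NIH stroke scale, mRS". Days 3 and 7 are absent, Day 14 is new, and no visit has a window.

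Statistical Data Analysis plans this test: "P values for difference among time point means (preoperative, postoperative days 3, 7 and 30) to be determined by ANOVA". It does not name the variable.

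End Points includes "Postop hematoma expansion" without naming the scans that define it. Data Points includes "width of hematoma on follow up imaging" without attaching a day.

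On events, the second objective is to determine whether the drug "reduces the rate of ipsilateral recurrence following drainage of chronic subdural hematomas", and Study Design names historical controls as the comparator. End Points lists same-sided return to the operating room and thromboembolic complications with no counting period. Timing of Evaluations lets follow-up run until the neurosurgeon releases the patient.

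**The concern.** A site using the evaluations list to book visits would take a Day 14 scan and no Day 3 or Day 7 scan. A site using Study Interventions would do the reverse. The ANOVA follows the second pattern. A scan that was not taken on Day 3 or Day 7 cannot be reconstructed, and the Day 14 scan taken instead enters no stated analysis. What can be seen of postoperative expansion also depends on which list was followed, because that endpoint is not tied to particular scans.

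The secondary issue is time at risk. If events are counted over an open-ended period that varies by patient, and the historical controls were observed for some other unstated period, the two proportions can differ with no drug effect at all.

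**Working it through.** There is no planned figure to reproduce: the documents give 50 patients without a power or precision calculation. The check is a comparison of the lists, followed by counts.

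**Postoperative days**

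| Source | Days |
|---|---|
| Study Interventions | 1, 3, 7, 30 |
| Clinical and Laboratory Evaluations | 1, 14, 30 |
| ANOVA, postoperative part | 3, 7, 30 |

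The first two lists agree on Days 1 and 30 and differ on Days 3, 7 and 14. ANOVA days missing from Study Interventions: none. ANOVA days missing from the evaluations list: 3 and 7. Both lists provide the preoperative and Day 30 points, so the evaluations list supplies 2 of the 4 ANOVA time points.

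**Which variable.** NIHSS and mRS are collected on Days 0 and 30 only. CT is the only outcome assessment assigned by name to Days 3 and 7. Hematoma size is therefore a strong inference, but it remains an inference.

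**Observations at stake.** Let f be the share of the 50 patients handled under the evaluations list alone, with no other missing scans.

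- Postoperative ANOVA observations: 3 × 50 − 2 × 50f = 150 − 100f.
- Patients with all four time points: 50(1 − f).

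| f | Postoperative observations | Patients with all four points |
|---|---|---|
| 0 | 150 | 50 |
| 0.5 | 100 | 25 |
| 1 | 50 | 0 |

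The documents do not give f. The three values show the range and are not estimates.

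**Does the ± 7 days reconcile the lists?** It may apply to Day 30 alone or to every listed day. If it applies to every day, Day 7 spans Days 0 to 14, so a Day 14 scan sits on its edge. Day 3 would span Day −4 to Day 10 and so contain Day 1, but Study Interventions lists Days 1 and 3 as separate scans. Four scheduled scans cannot be filled by three, so the conflict remains on either reading.

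**Event window.** Suppose events were counted to the Day 30 visit with its window. Time at risk would run from 23 to 37 days, a ratio of 37/23 = 1.61. Follow-up until release by the neurosurgeon sets no upper limit. The controls' period is not stated, so neither the size nor the direction of the resulting difference can be worked out from the documents.

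**The case against.** The best reply is that Study Interventions is worded as a requirement for all patients and that the ANOVA days all come from it. The evaluations list is terse and does not exclude Days 3 or 7, and taking all five scans would satisfy both sections. Much of this stands. It makes the repair easy and makes loss in every patient unlikely under proper conduct. It does not remove the conflict: no sentence gives one list precedence or says that they add together, and the evaluations section is a natural place for staff to look up visits.

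A reader might infer that the four-point test is lost for the whole trial. The documents do not support that, because f = 1 would mean not following Study Interventions in any of the 50 patients. A reader might also infer that the trial's main aim is compromised. It is not: the primary endpoint is drug-related complications, which do not depend on the CT list, and Day 30 volume is scheduled under both lists.

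On events, Day 30 is the last scheduled visit and the only day attached to an outcome, so a 30-day horizon is a plausible reading. It is nowhere stated, and the open-ended follow-up sentence points the other way. Data Points includes thromboembolic and other complications, and the latter could hold reoperations. The list may not be exhaustive, and some dates may be recoverable from clinical records.

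**Conclusion.** The schedule is internally inconsistent and should be corrected. Each patient handled under the evaluations list alone loses two of the three postoperative ANOVA time points for good. Across the trial the loss lies between 0 and 100 of 150 observations. This rests on two things: the inference that the ANOVA concerns hematoma size, and a share f that is unknown. The harm is confined to secondary imaging outcomes in a single-arm safety pilot.

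The missing event window is a real but secondary weakness that bears on the second objective. It would be tempting to say that the historical comparison is biased towards or against the drug. The documents support only that unequal follow-up could produce a difference in either direction.

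**What to change.** Put one schedule, with windows, into a single table that Study Interventions and Clinical and Laboratory Evaluations both cite, covering CTs and clinical visits. State which days the ± 7 days applies to. Make the ANOVA time points match the table and name the variable tested. State which scans define postoperative expansion. For patients already enrolled, report how many were scanned on each listed day. The choice of days is the sponsor's.

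For events:

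- Count return to the operating room and thromboembolic events to one prespecified postoperative day, defined by date and not by visit.
- Apply the same period to the historical controls.
- Censor patients followed for less time, using a time-to-event estimate, and report later events separately.
- Add return to the operating room, event dates and date of last contact to Data Points.
- If the controls' period cannot be established, report the comparison descriptively and say so.

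The cost is a short amendment and an edit to the data list. The number of postoperative scans in 50 patients depends on the sponsor's choice: 3 × 50 = 150 for the evaluations list, 4 × 50 = 200 for Study Interventions, or 5 × 50 = 250 for every listed day. Recurrences after the chosen counting day would leave the main proportion and be reported only separately, and event and last-contact dates must be collected or retrieved.

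### Applied literally, the flat 1300 mg preoperative dose and the 8-hour first postoperative dose exceed Table 1's once-daily renal doses on the first day

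*Combined protocol and SAP*

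**What the plan says.** The preoperative dose appears twice, both times as a flat 1300 mg. Study Enrollment has "Patients will receive a dose of 1300mg orally three to four hours prior to surgery"; Experimental Interventions, item 1, has "1300 mg times one immediately prior to surgery". Item 2 sets the standard postoperative regimen, "1300 mg orally three times daily for three days or until discharge- whichever comes first", and the line under it fixes its start: "First postop dosing will start 8 hours after preop dose is given".

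The renal rule follows. "All patients will have creatinine monitored daily while on study drug", and then "Patients with creatinine > 1.4 will have dosage adjustments as follows". Table 1 has three tiers:

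- Creatinine above 1.4 and up to 2.8: 1300 mg twice a day, Total Daily Dose 2600 mg.
- Above 2.8 and up to 5.7: "1300 mg (two 650 mg tablets) once a day for a maximum of 5 days during menstruation", Total Daily Dose 1300 mg.
- Above 5.7: "650 mg (one 650 mg tablet) once a day for a maximum of 5 days during menstruation", Total Daily Dose 650 mg.

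No sentence says whether the adjustment covers the preoperative dose, whether that dose counts toward the Total Daily Dose, or whether the 8-hour start still applies to a patient on once-daily dosing. Table 1 gives no time for the first postoperative dose.

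**The concern.** Two gaps meet in the same patients. The first is the preoperative dose. If it stays at 1300 mg whatever the creatinine, a patient above 5.7 has already received more than the table allows for the day. The second is the 8-hour start. It fits a three-times-daily schedule, but for a once-daily patient it places two doses within one 24-hour span.

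Such patients can be enrolled. The Exclusion Criteria do not name renal impairment, Table 1 provides for creatinine above 5.7, and the Supporting Data section cites a hemodialysis patient. The study's stated purpose is safety and its first endpoint is medication-related complications, so first-day dosing should not depend on who reads the order. The Data Points list names neither creatinine nor dose received, so the listed data would not show which reading was followed.

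Timing of the creatinine result adds to this. Monitoring is tied to the days on study drug, which include the day of the preoperative dose, but no sentence requires the result before that dose is given.

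**Working it through.** **Inputs.** Preoperative dose 1300 mg (Study Enrollment; Experimental Interventions, item 1); first postoperative dose 8 h later (line under item 2); tier doses, frequencies and daily totals (Table 1).

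**Step 1: reproduce Table 1's daily totals (dose × frequency).** 1300 × 2 = 2600 mg; 1300 × 1 = 1300 mg; 650 × 1 = 650 mg. All three agree with the table.

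**Step 2: standard regimen as a control.** Doses at 0, 8 and 16 h give 3 × 1300 = 3900 mg, the same as three times daily. The 8-hour line causes no conflict without renal adjustment.

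**Step 3: once-daily tiers.** Put the preoperative dose at 0 h and postoperative doses at h, h + 24 and h + 48. Sum the doses from 0 h up to, but not including, 24 h or 72 h, and divide by one or three times the Total Daily Dose. Take h = 8 if the 8-hour line applies, and h = 24 if the preoperative dose counts as that day's dose. The 72 h figures assume the patient is not discharged sooner.

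| Creatinine | Preop dose | h | First 24 h | Ratio | 72 h | Ratio |
|---|---|---|---|---|---|---|
| >2.8 to 5.7 | 1300 | 8 | 1300 + 1300 = 2600 | 2600/1300 = 2.0 | 4 × 1300 = 5200 | 5200/3900 = 1.33 |
| >2.8 to 5.7 | 1300 | 24 | 1300 | 1.0 | 3 × 1300 = 3900 | 1.0 |
| >5.7 | 1300 | 8 | 1300 + 650 = 1950 | 1950/650 = 3.0 | 1300 + 3 × 650 = 3250 | 3250/1950 = 1.67 |
| >5.7 | 1300 | 24 | 1300 | 1300/650 = 2.0 | 1300 + 2 × 650 = 2600 | 2600/1950 = 1.33 |
| >5.7 | 650 | 8 | 650 + 650 = 1300 | 2.0 | 4 × 650 = 2600 | 1.33 |
| >5.7 | 650 | 24 | 650 | 1.0 | 3 × 650 = 1950 | 1.0 |

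Of the 1950 mg, the preoperative dose supplies 1300/1950 = 67% and the 8-hour dose 650/1950 = 33%.

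**Step 4: duration.** With h = 8, every 24-hour window that opens after the preoperative dose holds one dose. The excess is therefore limited to the first day.

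**Step 5: calendar days instead of rolling 24 h.** A preoperative dose at 18:00 and a postoperative dose at 02:00 fall on different dates. Creatinine above 2.8 and up to 5.7 then shows 1300 mg on each date, with no excess. Above 5.7, the first date still shows 1300 mg against 650 mg (2.0), because the preoperative dose exceeds the total by itself.

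**Step 6: twice-daily tier.** If the 8-hour line applies and later doses are 12 h apart (an assumption; the plan gives no interval), doses at 0, 8 and 20 h total 3900 mg, and 3900/2600 = 1.5. Doses at 0 and 12 h total 2600 mg (1.0).

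The two preoperative timings, three to four hours before surgery or immediately before it, do not change these results, because the 8 hours run from the preoperative dose.

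**The case against.** The renal sentence is unqualified and follows the whole regimen: item 1, item 2, the 8-hour line, then the adjustment. On an ordinary reading a specific once-daily instruction displaces a start time written for three-times-daily dosing. A clinician who gave 1950 mg in a day to a patient above 5.7 would be acting against both the frequency and the daily total in the same table row. The rolling 24 hours is also this review's yardstick; the plan speaks only of daily dosing.

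Most of this stands. It removes the excess for creatinine above 2.8 and up to 5.7, and it shows that three times the daily total needs the least favourable combination: a table silent on the preoperative dose and an 8-hour line kept for a once-daily patient. It does not settle creatinine above 5.7. Displacing the 8-hour line still leaves a preoperative dose of 1300 mg against 650 mg, on a rolling or a calendar-day count, unless the adjustment is also read to cover a dose that is stated twice without qualification. Table 1 cannot decide that itself: its rows refer to menstruation and mention no preoperative dose.

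The investigators' general power to exclude unsuitable patients reduces the reach of the problem, but does not say how to dose those who are kept.

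A reader might also infer that creatinine is unknown at the first dose, because the Day 0 list omits it. The documents do not support that. The list need not be exhaustive and routine laboratory work may supply the value; only the order of test and dose is unstated.

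**Conclusion.** The conflict is real but narrow. Its firmest part is creatinine above 5.7, where the preoperative dose as written is twice the Total Daily Dose (1300 against 650 mg) before any postoperative dose; with the 8-hour dose the first rolling 24 hours reach 1950 mg. For creatinine above 2.8 and up to 5.7 the figure is 2600 against 1300 mg, and only if the 8-hour line is kept and days are counted as rolling 24 hours.

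These figures assume that the written sentences are applied literally and that the table governs only the doses after surgery. A reader might infer that the plan directs a threefold overdose, or that patients would be harmed. Neither follows. A no-excess reading is plausible in both tiers, although no sentence states it. The comparison is of milligrams with a table, and the documents give no exposure or toxicity data for one extra early dose. They also give no creatinine distribution, so the number affected among the 50 patients cannot be estimated and may be zero.

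**What to change.** 1. Require a creatinine result before the preoperative dose.
2. Limit the 8-hour sentence to the unadjusted three-times-daily regimen. For creatinine above 1.4, state that the preoperative dose counts toward the Total Daily Dose and that the next dose follows at the tier's interval: about 12 h for twice daily, 24 h for once daily.
3. For creatinine above 5.7, either give 650 mg preoperatively to match Table 1, or state that a single 1300 mg preoperative dose is an intended exception. This is a clinical choice, and the documents do not favour one option.

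With 650 mg chosen in item 3, first-24-hour totals are 2600, 1300 and 650 mg, equal to the table. Items 1 and 2 alone leave creatinine above 5.7 at 1300 mg, which is acceptable only as a declared exception.

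The editing cost is a few words, a footnote to Table 1 and one routine blood test. The clinical cost should be weighed openly. Against the 8-hour reading, first-24-hour drug falls by (2600 − 1300)/2600 = 50% for creatinine above 2.8 and up to 5.7. Above 5.7 it falls by up to (1950 − 650)/1950 = 67%, or (1950 − 1300)/1950 = 33% if the exception is kept. Once-daily patients would have no further dose until 24 h after the preoperative one. This affects only patients in these tiers.

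### The renal dosing table carries a five-day, menstruation-linked duration that does not match the trial's treatment period of three days or earlier discharge

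*Combined protocol and SAP*

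**What the plan says.** The general regimen is stated under Study Enrollment and again under Experimental Interventions. The latter gives a single preoperative dose, "1300 mg times one immediately prior to surgery", followed by "1300 mg orally three times daily for three days or until discharge- whichever comes first". Timing of Evaluations repeats the limit under Medication period: "Patients will continue on medication from immediately preoperatively to three days postoperatively or until discharge". None of these statements makes an exception for renal impairment.

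Experimental Interventions then introduces Table 1 with "Patients with creatinine > 1.4 will have dosage adjustments as follows". The Adjusted Dose column holds three entries, one per creatinine band (mg/dL):

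- above 1.4 up to 2.8: "1300 mg (two 650 mg tablets) two times a day for a maximum of 5 days during menstruation"
- above 2.8 up to 5.7: "1300 mg (two 650 mg tablets) once a day for a maximum of 5 days during menstruation"
- above 5.7: "650 mg (one 650 mg tablet) once a day for a maximum of 5 days during menstruation"

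A separate column gives the total daily dose: 2600, 1300 and 650 mg. The table mentions no stop at discharge. The inclusion criteria admit patients aged 18 to 85 undergoing intervention for a chronic subdural hematoma, with no restriction by sex.

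**The concern.** Table 1 is the operative instruction for any patient whose creatinine rises above 1.4, and its Adjusted Dose entries contain three things: a dose with its frequency, a maximum duration, and a condition. Only the dose and frequency plainly suit this trial. The duration differs from the one given everywhere else. Few enrolled patients could meet the condition: the Background reports the disease as far commoner above age 65 (up to 58 against 13.5 per 100,000 per year), and both sexes are eligible. The protocol does not say which parts of each entry are adopted, or which text prevails.

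The primary endpoint is medication-related complications in a 50-patient, single-arm safety study, so the dosing rule for patients with impaired renal function should not depend on inference. The Data Points list names neither creatinine nor the number of doses or days of drug taken. If a renal patient were treated for longer, the listed data would not show it.

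**Working it through.** The check is arithmetic on the protocol's own doses.

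**Step 1: the plan's own figures.** Daily dose = dose × doses per day.

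- Above 1.4 up to 2.8: 1300 × 2 = 2600 mg
- Above 2.8 up to 5.7: 1300 × 1 = 1300 mg
- Above 5.7: 650 × 1 = 650 mg

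All three agree with the table's Total Daily Dose column. The unadjusted daily dose is 1300 × 3 = 3900 mg, so the adjusted daily dose is 67%, 33% and 17% of it.

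**Step 2: the unadjusted course.** Postoperative total = daily dose × days = 3900 × 3 = 11,700 mg. This is nine doses, with no early discharge.

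**Step 3: the adjusted course under each reading.**

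| Creatinine band | 3 days | % of 11,700 mg | 5 days | % of 11,700 mg |
|---|---|---|---|---|
| above 1.4 up to 2.8 | 2600 × 3 = 7,800 mg | 67% | 2600 × 5 = 13,000 mg | 111% |
| above 2.8 up to 5.7 | 1300 × 3 = 3,900 mg | 33% | 1300 × 5 = 6,500 mg | 56% |
| above 5.7 | 650 × 3 = 1,950 mg | 17% | 650 × 5 = 3,250 mg | 28% |

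Adding the 1300 mg preoperative dose to both courses changes the first band's five-day comparison to 14,300 against 13,000 mg (110%).

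**Step 4: break-even.** Days at which the adjusted total equals the unadjusted total = 11,700 / adjusted daily dose: 4.5 days in the first band, 9 in the second, 18 in the third. A five-day ceiling passes break-even in the first band only.

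**Step 5: sensitivity to dose counting.** The protocol also says "First postop dosing will start 8 hours after preop dose is given", and the Medication period runs to three days after surgery. Doses on the day of operation could therefore bring the unadjusted count above nine. Against a first-band total of 13,000 mg:

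- 9 doses: 9 × 1300 = 11,700 mg; ratio 1.11
- 10 doses: 10 × 1300 = 13,000 mg; ratio 1.00
- 11 doses: 11 × 1300 = 14,300 mg; ratio 0.91

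**Step 6: the texts side by side.** On duration, five days exceeds three in every band. On stopping, the general regimen ends at discharge and the table is silent. On condition, the general regimen has none and the table requires menstruation.

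**The case against.** The strongest reply is that a ceiling is not a course. Three days of treatment satisfies a five-day maximum, and the Medication period, which comes after the table and makes no renal exception, can be read as limiting every patient to three days or earlier discharge. Taken together, the statements would then give one duration and no excess exposure. To arrive at five days, a reader would have to drop the menstruation condition, keep the five days as a target, and set the Medication period aside. This objection largely stands: the documents permit the longer course but do not direct it. It does not settle the matter, because the combined reading is an inference that the protocol never states, and it leaves the menstruation condition unexplained.

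A reader might go further and infer that any patient with creatinine above 1.4 could receive more drug than a patient with normal creatinine. The documents do not support that. Daily dose falls in every band, and total dose can be higher only in the first band, only near the five-day ceiling, and only if the unadjusted course is nine doses.

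Nor can one say that the longer course exceeds what was intended, since that presumes which duration is right. It is also fair to say that mixed treatment durations are not new here: stopping at discharge already makes duration vary between patients.

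**Conclusion.** The inconsistency is real and present in all three rows of Table 1: a duration, and a condition unsuited to this population, that do not match the treatment period given elsewhere, with no rule of precedence. Its consequence is conditional.

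- **If the five-day ceiling is used as the duration**, the course can be two days longer than the unadjusted one in every band. Total postoperative dose can exceed the unadjusted total only for creatinine above 1.4 up to 2.8, by about 11% on nine unadjusted doses. That excess disappears at ten doses and reverses at eleven.
- **If the Medication period caps all patients**, there is no excess in days or dose, and the remaining defect is a condition that does not fit the patients the table governs.

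The totals assume no discharge before the stated number of days and a creatinine that stays in one band. The documents do not give the share of patients above 1.4, so the number affected in a sample of 50 cannot be stated. The point merits correction because it sits in a dosing instruction of a safety study and is cheap to resolve. It does not show that any patient would be overdosed.

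**What to change.** Reconcile Table 1 with the regimen under Study Enrollment and Experimental Interventions and with the Medication period under Timing of Evaluations. In all three rows, replace the duration and menstruation wording with one duration, one stopping statement and any condition that the sponsor chooses, worded consistently in each place. State explicitly whether the table changes only dose and frequency or also duration. The choice belongs to the sponsor and the investigators; no view is given here on which duration or dose is right.

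The cost is one table edit by protocol amendment, with no extra patients or procedures.
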